4.1 Objectives

4.1.1 Primary objective

To confirm the effect of continuous subcutaneous insulin infusion (CSII) treatment with fasteracting insulin aspart in terms of glycaemic control by comparing it to CSII treatment with NovoRapid[®], in adults with Type 1 Diabetes Mellitus (T1DM), using a non-inferiority approach.

4.1.2 Secondary objectives

To confirm superiority of CSII treatment with faster-acting insulin aspart compared to CSII treatment with NovoRapid[®] in adults with T1DM, in terms of:

- Postprandial glucose regulation (meal test)
- Overall glycaemic control (HbA_{1c})
- Postprandial glucose excursions (1,5-anhydroglucitol)
- Time spent in low interstitial glucose (CGM)

To compare the effect and safety of CSII treatment with faster-acting insulin aspart vs. CSII treatment with NovoRapid[®] in adults with T1DM.

4.2 Endpoints

Baseline is defined as randomisation (Visit 6).

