A total of approximately 666 Subjects with T1DM are planned to be screened, approximately 506 Subjects to enter the run-in period, of which 450 are expected to enter randomised treatment.

Protocol Date: 04 February 2016 Novo Nordisk
Trial ID: NN1218-3854 Version: 4.0

Final

14 of 149

 Trial ID: NN1218-3854
 Version:

 UTN: U1111-1118-2480
 Status:

 EudraCT no.: 2010-024054-11
 Page:

Key inclusion criteria

- Male or female, age \geq 18 years at the time of signing the informed consent
- Diagnosed with T1DM ≥ 1 year prior to the day of screening
- Using the same Medtronic pump (Minimed 530G (551/751), Paradigm Veo (554/754), Paradigm Revel (523/723), Paradigm (522/722)) for CSII in a basal-bolus regimen with a rapid acting insulin analogue for at least six months prior to screening and willing to stay on the same pump model throughout the trial (if the model is changed the change should not exceed 7 consecutive days.)
- HbA_{1c} 7.0-9.0% (53-75 mmol/mol) as assessed by central laboratory at screening
- Body mass index (BMI) $\leq 35.0 \text{ kg/m}^2$ at screening
- Ability and willingness to take at least 3 daily meal-time insulin bolus infusions every day throughout the trial

Key exclusion criteria

- Any of the following: myocardial infarction, stroke, hospitalization for unstable angina or transient ischaemic attack within the past 180 days prior to the day of screening
- Planned coronary, carotid or peripheral artery revascularisation known on the day of screening
- History of hospitalization for ketoacidosis ≤180 days prior to the day of screening
- Treatment with any medication for the indication of diabetes or obesity other than stated in the inclusion criteria in a period of 90 days before screening
- Any condition which, in the opinion of the Investigator, might jeopardise a Subject's safety or compliance with the protocol

Key efficacy assessments

- HbA_{1c}
- PPG increments (meal test)
- 1,5-anhydroglucitol
- IG measurements (CGM)

Key safety assessments

- Number of treatment emergent hypoglycaemic episodes
- Number of adverse events

Trial products

• Faster-acting insulin aspart, 100 U/mL solution for subcutaneous (s.c.) infusion provided in 10 mL vial (Investigation Medicinal Product (IMP)– blinded)

Protocol		Date:	04 February 2016	Novo Nordisk
Trial ID: NN1218-3854	CONFIDENTIAL	Version:	4.0	
UTN: U1111-1118-2480	CONFIDENTIAL	Status:	Final	
EudraCT no.: 2010-024054-11		Page:	15 of 149	

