5.3 Treatment of Subjects

At the start of the run-in period (Visit 2), Subjects will remain on their pre-trial insulin treatment. At randomisation (Visit 6), Subjects will be switched from their current insulin treatment to either faster-acting insulin aspart or NovoRapid[®] in a 1U:1U manner, keeping the current insulin delivery parameters in the pump. After the transfer to trial insulin treatment the insulin pump delivery parameters should be reviewed with regards to the need for adjustments. During the run-in period (Visit 2 to Visit 6), the basal rates and Bolus Wizard[®] should not be adjusted unless indicated for safety reasons.

In the treatment period starting at randomisation (Visit 6), the Investigators must strive to achieve a glycaemic target of fasting and pre-prandial BG between 4.0-6.0 mmol/L [71-108 mg/dL] in a treat-to-target fashion based on frequent SMPG profiles and safety. No maximum dose of insulin is specified. All Subjects will perform at least 4-point SMPG profiles on a daily basis, in accordance with section 8.3.2.2, throughout the trial. Guideline documents for the management of Insulin Pump Therapy will be provided both to the Investigators and the Subjects 20.21.

The dose adjustments must be done based on SMPG values only. No other anti-diabetic medication except the current insulin treatment is allowed during the trial after start of run-in period (Visit 2) until randomisation (Visit 6). No other insulin products except the trial medication are allowed from start of the randomisation (Visit 6) until end of treatment (Visit 22).

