6.2 Inclusion criteria

For an eligible Subject, all inclusion criteria must be answered "Yes".

- 1. Informed consent obtained before any trial-related activities. Trial-related activities are any procedures that are carried out as part of the trial, including activities to determine suitability for the trial
- 2. Male or female, age ≥ 18 years at the time of signing informed consent
- 3. Diagnosed with T1DM \geq 1 year prior to the day of screening
- 4. Using the same Medtronic pump (Minimed 530G (551/751), Paradigm Veo (554/754), Paradigm Revel (523/723), Paradigm (522/722)) for CSII in a basal-bolus regimen with a rapid acting insulin analogue for at least six months prior to screening and willing to stay on the same pump model throughout the trial (if the model is changed the change should not exceed 7 consecutive days.)
- 5. Ability and willingness to refrain from using low glucose suspend mode in the pump throughout the trial
- 6. Willingness to use one of the following types of infusion sets: Medtronic Quick-Set[®], Medtronic Mio[®], Medtronic Silhouette[®] or Medtronic Sure-T[®] (Easy-set[®]) throughout the trial
- 7. Willing to use CSII as the insulin treatment during the entire trial
- 8. Using the same insulin for at least 90 days prior to screening
- 9. HbA_{1c} 7.0-9.0% (53-75 mmol/mol) inclusive as assessed by central laboratory at screening
- 10. BMI \leq 35.0 kg/m² at screening

Protocol	Date:	04 February 2016	Novo Nordisk
Trial ID: NN1218-3854	Version:	4.0	

 Trial ID: NN1218-3854
 CONFIDENTIAL
 Version: 4.0

 UTN: U1111-1118-2480
 Status: Final

 EudraCT no.: 2010-024054-11
 Page: 34 of 149

11. Ability and willingness to take at least 3 daily meal-time insulin bolus infusions every day throughout the trial

12. Ability and willingness to adhere to the protocol including performing SMPG profiles, CGM and meal test

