8.1.2 Screening visit

At screening (Visit 1), each Subjects will be assigned a unique 6-digit Subject number which will remain the same throughout the trial. A screening session must be performed in the IV/WRS.

Subjects will continue on their current diabetes treatment until start of randomisation (Visit 6) and they will not be supplied with any trial products until then.

Any abnormal and clinically significant findings at Visit 1 must be recorded on the medical history/concomitant illness form in the electronic case report form (eCRF).

At screening, Subjects will be provided with a card (Subject Participation Card) stating that they are participating in a trial and given contact address(es) and telephone number(s) of relevant trial site staff. Subjects should be instructed to return the card to the Investigator at last trial visit or to destroy the card after the last visit.

Protocol		Date:	04 February 2016	Novo Nordisk
Trial ID: NN1218-3854	CONFIDENTIAL	Version:	4.0	
HTN: H1111-1118-2480	CONFIDENTIAL	Status:	Final	

Page:

41 of 149

The Investigator must keep a Subject Screening Log, a Subject Identification Code List and a Subject Enrolment Log. The Subject Screening Log and Subject Enrolment Log may be combined in one list.

For screening (Visit 1) procedures, please see flowchart in section $\underline{2}$.

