8.4 Laboratory assessments

Except for urine pregnancy testing, ketone measurements (blood/urine, in case of a hyperglycaemic episode) which will be performed locally, all laboratory analyses will be performed by a central laboratory contracted by Novo Nordisk. The central laboratory will provide all laboratory supplies for the sampling and transportation of all blood and urine samples taken during the trial. The central laboratory may utilise subcontractors.

A detailed description of the assay methods, reference ranges and procedures for obtaining the samples, handling, storage and shipment of the samples are specified in a trial-specific laboratory manual provided to the sites by the central laboratory. Information regarding laboratory materials such as tubes and labels are also described in there.

Laboratory samples can be drawn on another day than on the day of the actual visit, as long as it is within the visit window, as stated in the flowchart in section 2.

If laboratory samples need to be retaken due to missing result(s) (e.g. haemolysed, sample leaked during transit, sample not being conclusive, lost in transit, etc.), the Subject should be called in for resampling. Please see the laboratory manual for further guidance. The repeated blood sampling must be marked with the related visit number and missing lab measurements. The laboratory sample date must be recorded in the eCRF should reflect the actual date of sampling (i.e. the actual visit date will differ from the assessment date under the same visit.)

Only laboratory samples specified in the protocol should be sent to the central laboratory for analysis. If additional laboratory sampling is needed, e.g. to follow up on AEs, this should be done at the local laboratory. Samples for the central laboratory will be coded in order to keep Subject's identity anonymous.

Laboratory results will be made available by the central laboratory. The laboratory provides results to the trial sites in the units preferred by the trial sites while the results that are transferred to the trial database will always be in SI units.

Protocol	Date:	04 February 2016	Novo Nordisk
Trial ID: NN1218-3854	Version:	4.0	

UTN: U1111-1118-2480 CONFIDENTIAL Status: Final Page: 71 of 149

Final laboratory reports must be reviewed, dated and signed by the Investigator on the day of evaluation. It must be specified by the Investigator whether out of range results are clinically significant.

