8.4.5 HbA_{1c}

Blood samples will be drawn as specified in the flow chart (section 2) to determine the HbA_{1c} level in order to evaluate glycaemic control.

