- For each of the complete data sets, the change from baseline to week 16 is analysed using an analysis of variance model with treatment, strata, previous insulin use and region as factors, and baseline HbA_{1c} as a covariate.
- The estimates and standard deviations for the 100 data sets are pooled using Rubin's formula:

$$m_{MI} = \frac{1}{100} \sum_{i=1}^{100} m_i ,$$

$$SD_{MI} = \sqrt{\frac{1}{100} \sum_{i=1}^{100} SD_i^2 + \left(1 + \frac{1}{100}\right) \left(\frac{1}{100-1}\right) \sum_{i=1}^{100} (m_i - m_{MI})^2}$$

where m_i and SD_i are the estimated means and standard deviations for the 100 copies of the dataset, and m_{MI} and SD_{MI} are the pooled estimates.

- From m_{MI} and SD_{MI} , the 95% confidence interval for the treatment differences is calculated.

Non-inferiority of fast-acting insulin aspart will be considered confirmed if the upper boundary of the two-sided 95% CI is below or equal to 0.4% or equivalent if the p-value for the one-sided test of

$H_0: D > 0.4\%$ against $H_A: D \leq 0.4\%$,

is less than or equal to 2.5%, where D is the mean treatment difference (fast-acting insulin aspart minus NovoRapid[®]).

Note that as the anticipated number of Subjects discontinuing treatment, but not trial is low, imputations based on such Subjects will not be suitable.

Provided that the hierarchical testing allows, the evaluation of superiority will be based on the same statistical model, as the primary analysis 1). The associated sensitivity analysis that follows will investigate the robustness of non-inferiority and superiority (analysis 3b and 3c) as well.

Sensitivity analyses for the primary analysis addressing the primary estimand

All sensitivity analyses for the primary analysis addressing the primary estimand will use the in-trial observation period.

- 2) First the primary analysis in 1) will be repeated, but excluding all factors except from treatment from the multiple imputation and analysis of variance models while still including baseline HbA_{1c} as a covariate. This analysis will explore the influence of the different factors.

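### Free improvement: the primary and Step 3 HbA1c model could also adjust for the screening (Visit 1) HbA1c, which is already collected; the likely gain is small

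*Protocol*

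**What the plan says.** Protocol 4.2: "Baseline is defined as randomisation (Visit 6"). Protocol section 17 and SAP section 2 repeat this. They use an earlier value only when the Visit 6 value is missing, and otherwise limit pre-randomisation data to descriptive summaries.

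SAP 2.3, analysis 1) fits week-16 change in HbA1c with "treatment, strata, previous insulin use and region as factors, and baseline HbA_{1c} as a covariate". The sequential imputation models also carry one baseline HbA1c. Step 3 reads its result from the same confidence interval (Protocol 17.4.1, SAP 2.4.1). The changes listed in SAP section 3 add no second HbA1c covariate.

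The flow chart (Protocol section 2) marks HbA1c at Visit 1 (week -6) and Visit 6 (week 0). Inclusion criterion 9 requires 7.0-9.0% "inclusive as assessed by central laboratory at screening". Protocol 8.4 says that, apart from a few local tests, "all laboratory analyses will be performed by a central laboratory contracted by Novo Nordisk".

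On treatment between the two samples, Protocol 8.1.2 says "Subjects will continue on their current diabetes treatment until start of randomisation (Visit 6"). Protocol 5.3 says that run-in pump settings "should not be adjusted unless indicated for safety reasons".

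**The concern.** Week-16 HbA1c depends on the subject's underlying level, and one reading at Visit 6 measures that level with some assay and short-term variation. Whatever Visit 6 misses stays in the residual variance. A second pre-randomisation reading on the same insulin could recover part of it, and treatment cannot have affected it.

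Step 3 is where this could count. The trial is sized for Steps 1 and 2 only (Protocol 17.1), Step 3 has low power on the plan's own inputs, and Steps 4 and 5 can be tested only if Step 3 succeeds.

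**Working it through.** **Plan's figures.** Two-group t-test, noncentral t, 225 per arm (Protocol 17.1):
- Step 1: difference -0.1, margin 0.4, SD 0.8, one-sided 2.5%. Power is above 99.9%, as stated.
- Step 2: difference 0.9, SD 3.4, two-sided 5%. Power is 80.0%, as stated.
- Step 3 (no power stated): difference -0.1, SD 0.8, two-sided 5%. SE = 0.8 × √(2/225) = 0.0754 and power = 26.3%. About 1005 per arm would be needed for 80%.

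**Gain from Visit 1, treating the two readings as replicates.** Assumptions, not in the documents: between-subject variance v_T = 0.25-0.36 (SD 0.5-0.6%) and within-subject variance v_e = 0.0225-0.09 (SD 0.15-0.3%).
- Unexplained variance of the true level given Visit 6: v_T·v_e/(v_T + v_e).
- Given both readings: 1/(1/v_T + 2/v_e).
- r = (first minus second)/(residual SD)². Equivalent extra subjects = 450 × (1/(1 − r) − 1).

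With residual SD 0.8 (variance 0.64):
- Low end (SDs 0.5 and 0.15): 0.02064 − 0.01077 = 0.0099; r = 1.5%; about 7 subjects; Step 3 power 26.6%.
- High end (SDs 0.6 and 0.3): 0.0720 − 0.0400 = 0.0320; r = 5.0%; about 24 subjects; Step 3 power 27.4%.

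**If 0.8 is the SD of the raw change**, as Protocol 17.1 describes it, the high end gives residual variance 0.64 − 0.09 + 0.072 = 0.622 with Visit 6 and 0.64 − 0.09 + 0.040 = 0.590 with both. Step 3 power goes from 26.9% to 28.1%.

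**Smaller residual SD.** At 0.5 the high end gives r = 0.032/0.25 = 12.8%. Simulating the 7.0-9.0% restriction on Visit 1 (assumed untruncated mean 8.0%) lowers this to about 10%. At residual SD 0.8 the restriction lowers 5.0% to about 3.9%.

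**Correlations instead of variance components** (also assumed). The reduction is the squared partial correlation of Visit 1 with week 16 given Visit 6. Take Visit 1–Visit 6 = 0.8 and Visit 6–week 16 = 0.7:
- Visit 1–week 16 of 0.56 (= 0.8 × 0.7): reduction 0.
- Visit 1–week 16 of 0.65: (0.65 − 0.56)/√(0.36 × 0.51) = 0.21, reduction 4.4%.
- Visit 1–week 16 of 0.70: reduction 10.7%.

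The favourable case sets all three correlations equal (0.6-0.8). With Visit 1 truncated to 7.0-9.0% it gives 5-16%, and 6.9% in the setting whose SD of change (0.805) is closest to the plan's. At residual SD 0.8, a 10% reduction gives Step 3 power of 28.6% and a 15% reduction gives 30.0%.

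**The case against.** The strongest case against is that nothing is wrong. One randomisation baseline is a standard, valid choice, stated consistently in both documents, and restricting earlier data to description is also a stated choice. At the plan's SD the gain is about one power point or less, on a step that is reached only after Step 2 and that the trial was not sized for. All of this stands, and it is why the point is only a free improvement.

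Three stronger readings are tempting, and the documents support none of them.
- A reader might infer that the primary analysis is biased or misspecified. It is not: adjusting for Visit 6 gives a valid treatment contrast.
- A reader might treat the two values as replicates and take a large gain from that. The rule on pump settings covers only Visit 2 to Visit 6, and Visit 2 may come up to 17 days after Visit 1. From Visit 2, subjects receive a BG meter, daily 4-point profiles, pump training and reinforced carbohydrate-counting training (Protocol 8.3.2.2, 8.3.2.4, 8.3.2.5), and safety adjustments are allowed. Visit 6 may therefore reflect a changed state. The 12.8% figure also needs a residual SD of 0.5 and ignores the eligibility range.
- A reader might infer that the covariate would rescue Step 3. It would not, under any of the assumptions tried.

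The objection does not remove the point, because the change needs no replicates. Visit 1 would get its own coefficient. If it adds nothing, that coefficient is near zero and one degree of freedom is lost.

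**Conclusion.** Holds as a free improvement, not as an error. Screening HbA1c is available for every properly included subject and the model leaves it out. Using it would not change the endpoint, the estimand or the type I error, provided that it is prespecified.

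The size rests on assumed variance components, because the documents report no HbA1c correlations. At the plan's SD of 0.8 as residual SD, residual variance falls by about 1.5-5% and Step 3 power rises from 26.3% to about 26.6-27.4%. At residual SD 0.5, with the 7.0-9.0% restriction, the reduction is up to about 10%. It could be near zero if Visit 6 already carries the information. Step 1 stays above 99.9%, Step 2 concerns a different endpoint, and Step 3 remains well below 80% either way.

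**What to change.** In SAP 2.3, analysis 1), before unblinding:
- Add screening (Visit 1) HbA1c as a second covariate in the sequential imputation models and in the week-16 analysis model.
- Enter it as a separate term. Do not average it with Visit 6, because the screening value was used for selection.
- Carry it into analyses 3) to 7). Step 3 inherits it through analysis 1).
- Keep change from Visit 6 as the endpoint.
- State that where Visit 6 is missing and Visit 1 is substituted as baseline, the same value fills both terms.

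The cost is one model term and one degree of freedom, with no added data collection.

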4.2.1 Primary endpoint

Change from baseline in glycosylated haemoglobin (HbA_{1c}) 16 weeks after randomisation.

4.2.2 Confirmatory secondary endpoints

- Change from baseline in 1-hour PPG increment 16 weeks after randomisation (meal test)
- Change from baseline in 1,5-anhydroglucitol 16 weeks after randomisation
- Change from baseline of time spent in low IG (≤3.9 mmol/L [70 mg/dL]) during CGM 16 weeks after randomisation

4.2.3 Supportive secondary endpoints

Supportive secondary endpoints are detailed in section 17.4.2 and are therefore only listed below without a detailed explanation.

 Trial ID: NN1218-3854
 Version:
 4.0

 UTN: U1111-1118-2480
 Status:
 Final

 EudraCT no.: 2010-024054-11
 Page:
 25 of 149

4.2.3.1 Supportive secondary efficacy endpoints

16 weeks after randomisation:

- Change from baseline in fasting plasma glucose (FPG)
- Percentage of Subjects reaching HbA_{1c} targets
 - HbA_{1c} < 7.0% (53 mmol/mol)
 - HbA_{1c}<7.0 % (53 mmol/mol) without severe hypoglycaemic episodes
- Change from baseline in 30- min, 1- hour, 2- hour, 3- hour and 4- hour PPG and in 30- min, 2- hour, 3- hour and 4- hour PPG increment 16 weeks after randomisation (meal test)
- Change from baseline in 7-7-9 point self-measured plasma glucose (SMPG) profile assessed by:
 - Mean of the 7-7-9 point SMPG profile
 - PPG and PPG increment (mean, breakfast, lunch and main evening meal)
 - Pre-prandial plasma glucose (PG) (mean, pre-breakfast, pre-lunch, pre-main evening meal)
 - Fluctuation in 7-7-9 point profile
 - Change in nocturnal SMPG measurements
- Percentage of Subjects reaching PPG target (overall mean of daily post prandial glucose measurements in 7-7-9-point self-measured plasma glucose):
 - Overall PPG (1 hour) \leq 7.8 mmol/L [140 mg/dL]
 - Overall PPG (1 hour) \(\leq 7.8\) mmol/L [140 mg/dL] without severe hypoglycaemia
- Change from baseline in lipids-lipoproteins profile (total cholesterol, high density lipoproteins, low density lipoproteins)
- Insulin dose (Units/day and Units/kg/day; total basal, total bolus, total daily insulin dose and individual meal insulin dose):
- Insulin delivery pump parameters including insulin carbohydrate ratio, glucose sensitivity factor and active insulin time

4.2.3.2 Supportive secondary CGM and meal characteristics related endpoints excluding meal test

16 weeks after randomisation:

- Change from baseline in mean IG increment (0-30 min, 0-1 hour and 2 hours after start of meal)
- Change from baseline in mean time to the IG peak after start of meal

Protocol		Date:	04 February 2016	Novo Nordisk
Trial ID: NN1218-3854	CONFIDENTIAL	Version:	4.0	
UTN: U1111-1118-2480	CONFIDENTIAL	Status:	Final	
EudraCT no.: 2010-024054-11		Page:	26 of 149	

Page:

Change from baseline in mean IG peak after start of meal

4.2.3.3 Supportive secondary endpoints CGM related endpoints excluding meal test

16 weeks after randomisation:

- Percentage of time spent with IG ≤ 2.5 , 3.0, 3.5 mmol/L [45, 54, 63 mg/dL]) and IG ≥ 10.0 , 12.0 mmol/L [180, 216 mg/dL])
- Incidence of episodes with IG $\leq 2.5, 3.0, 3.5, 3.9 \text{ mmol/L} [45, 54, 63, 70 \text{ mg/dL}])$ and IG >10.0, 12.0 mmol/L [180, 216 mg/dL])
- Change from baseline in mean of the IG profile
- Percentage of time spent within target range 4.0-7.8 mmol/L (71-140 mg/dL)
- Variation in the IG profile
- Area under the curve (AUC_{3.9-IG}) for IG \leq 3.9 mmol/L [70 mg/dL]

4.2.3.4 Supportive secondary endpoints related to CGM and meal test

16 weeks after randomisation:

- Change from baseline in AUC_{IG.0-15min}
- Change from baseline in AUC_{IG.0-30min}
- Change from baseline in AUC_{IG.0-1h}
- Change from baseline in AUC_{IG.0-2h}
- Change from baseline in AUC_{IG-0-4h}
- Change from baseline in time to the IG peak after start of meal
- Change from baseline in IG peak after start of meal

 Trial ID: NN1218-3854
 Version:
 4.0

 UTN: U1111-1118-2480
 Status:
 Final

 EudraCT no.: 2010-024054-11
 Page:
 27 of 149

